1.3 Analysis populations

All analyses and data summaries will be conducted on the intention-to-treat (ITT) population which is defined as all enrolled participants and followed up at least for 3 days in ICU, and also critical care

Single-used versus MultiPIE-used endotracheal suCtIon cAtheters in mechanically ventiLated ICU patients: the SPECIAL-ICU trial. Statistical Analysis Plan Version 1 dated 14th of December 2023.

nurses who conducted the study. Withdrawn Patients and critical care nurses who will refuse to be interviewed will not be included in the analysis.

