1.5 Outcome analysis

As a feasibility study, analysis will focus on descriptive statistics and confidence interval (CI) estimation rather than formal hypothesis testing.

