1.6 Primary analysis

The aim of this primary analysis is to assess the feasibility of delivering the intervention in the study settings, and selection of primary and secondary outcome measures. Components to be analysed are:

feasibility of a trial by producing:

- CONSORT diagram
- Timing of follow-up assessments
- Time it took to recruit participants
- Number of critical care nurses willing to participate
- Randomization technique effectiveness

feasibility of the intervention by producing:

- Critical care nurses' acceptability of the intervention
- Method of delivering the intervention to each study arm

Selection of primary/secondary outcomes

comparing outcomes of each study group

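### SAP section 1.3 gives the name intention-to-treat to a three-day evaluable set that also drops withdrawn patients, so their collected day-3 data leave the by-arm comparison

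*SAP*

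**What the plan says.** Section 1.3 of the SAP sets one population for everything: "All analyses and data summaries will be conducted on the intention-to-treat (ITT) population". It defines that population as the "intention-to-treat (ITT) population which is defined as all enrolled participants and followed up at least for 3 days in ICU", and it adds the nurses who took part. It then states: "Withdrawn Patients and critical care nurses who will refuse to be interviewed will not be included in the analysis". The SAP defines no other analysis population. This point concerns the patients only.

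Four other statements bear on it:

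- Section 1.2 places the first evaluation on ICU day 3 and the second on day 6. It plans a modified CPIS for every participant so that VAP can be compared between groups, and it sets significance at P ≤ 0.05.
- Section 1.2 also plans an extended CONSORT diagram running from screening to follow-up, and it estimates follow-up at 50% or more. Section 1.1 plans 60 participants.
- Section 1.5 says that "analysis will focus on descriptive statistics and confidence interval (CI) estimation rather than formal hypothesis testing".
- Section 1.6 lists "Randomization technique effectiveness" among the feasibility components, and "comparing outcomes of each study group" as the basis for choosing outcomes.

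**The concern.** Intention-to-treat means that participants are analysed as randomised, whatever happens to them afterwards. The set in section 1.3 is selected on two things that can happen afterwards: reaching three days of ICU follow-up, and not withdrawing. The name and the content do not match, and nothing elsewhere in the SAP corrects the name.

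Two things are at stake. First, the report would carry a claim of ITT analysis that the plan does not deliver. Second, a patient who is scored on day 3 and withdraws before day 6 has an outcome measurement, yet the rule removes that patient from the by-arm VAP results. Those results feed the choice of outcomes (1.6) and the sample size of the later trial (1.1). They are also tested between groups (1.2), so a selective loss could affect P values as well as descriptive tables.

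**Working it through.** **1. Definition against label.** The SAP gives no formula or figure for this set, so there is nothing to reproduce. The check is a comparison of texts.

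| Element | ITT in the usual sense | SAP section 1.3 |
|---|---|---|
| Who enters | All randomised, by allocated arm | Enrolled, with at least three days of ICU follow-up |
| Withdrawn patients | Kept, with data up to withdrawal | Removed |
| Scope | Usually the main analysis | Every analysis and summary |

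The label would be accurate only if two things both held: the three-day condition removes nobody after allocation, and withdrawal means that permission to use the data was revoked. The SAP states neither.

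**2. What the withdrawal rule does to VAP.** In one arm, take the patients with a day-3 score. Let *w* be the share of them who later withdraw, and *d* the VAP proportion in those withdrawn minus that in those kept. Then

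p_all = (1 − w) × p_kept + w × p_withdrawn = p_kept + w × d.

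Restoring the withdrawn patients moves the arm's proportion by w × d. The SAP gives neither quantity. The values below are assumptions that show how the formula behaves; they do not estimate or bound the bias.

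| w (assumed) | d = 0 | d = ±20 points (assumed) |
|---|---|---|
| 5% | 0 | ±1 point |
| 10% | 0 | ±2 points |
| 25% | 0 | ±5 points |

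The difference between two arms moves by w1 × d1 − w2 × d2. If w and d are equal in both arms, this is zero: the VAP level may shift but the contrast does not. With w1 = 25%, w2 = 5% and d = +20 points in both arms, it is 5 − 1 = 4 points.

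**3. Whether the plan's figures cap the effect.** With 60 participants and 50% follow-up, 60 × (1 − 0.50) = 30 are lost across the trial. This does not limit *w* in an arm, for three reasons:

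- The 30 need not be spread evenly. Section 1.2 mentions three groups. If these were equal arms of 60 / 3 = 20 (an assumption), one arm could lose all 20 and the total would still be within 30.
- The 50% has no stated time point. If it refers to day 6, patients lost between days 3 and 6 without withdrawing stay in the section 1.3 set, so 30 is not the size of that set either.
- Losses before day 3 leave no CPIS to restore and do not enter *w*.

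**4. Follow-up rates.** Inside a set that requires three days of follow-up, day-3 retention is 100% by construction, whatever the true figure out of 60. A follow-up or withdrawal rate is informative only with all randomised participants as the denominator.

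**The case against.** The strongest reply is that the three-day condition has an evident reason. The first evaluation falls on day 3, section 1.2 sets a three-day minimum, and a patient lost earlier has no CPIS under any definition. That stands. It supports using such a set for VAP, but it does not support calling the set ITT, and it gives no reason to remove patients who have been scored and then withdraw.

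It is also fair to say that the timing of randomisation and the meaning of withdrawal may be in the protocol, which was not available for this review. If allocation falls at or near day 3, and withdrawal means revoked consent, little remains beyond the label. Their absence from the SAP is not counted as a fault here.

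A reader might infer that section 1.3 makes the feasibility outputs impossible. The SAP does not support that:

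- The "CONSORT diagram" has its own provision in section 1.2, starting from screening. Screened patients could not belong to an enrolled set on any reading, and losses after allocation would be visible in the diagram.
- "Time it took to recruit participants" can be taken from recruitment dates and needs no patient analysis set.
- "Randomization technique effectiveness" is undefined. If it means allocation counts, the diagram supplies them. Only if it includes something like baseline balance does the restricted set matter.

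Finally, this is a feasibility study whose stated emphasis is descriptive. That lowers the stakes, but it does not remove them, because section 1.2 still plans between-group tests.

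**Conclusion.** The point holds in two parts. With high confidence, section 1.3 misnames its population: the set is evaluable or modified ITT. Conditionally, the rule discards day-3 outcome data from withdrawn patients, and so affects the by-arm VAP summaries, intervals and tests. The condition is that withdrawal does not mean revoked consent to data use.

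Whether bias follows depends on facts that the SAP does not give. If withdrawal is unrelated to outcome, there is none. If it is related to outcome in the same way and to the same extent in every arm, the VAP level can be off but the comparison is not. If it also differs by arm, the comparison can be off. Neither size nor direction can be derived.

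It is tempting to turn the 50% follow-up estimate into a statement that up to half of each arm is dropped, or into a maximum shift in VAP. The document does not support this: the figure is trial-wide, has no time point and does not separate withdrawal from other loss.

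The point should be corrected before analysis. It does not call the trial's feasibility aims into question.

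**What to change.** In section 1.3:

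- Define ITT as all randomised participants in their allocated arm. Keep data collected up to withdrawal unless consent to use them is revoked.
- Use that set as the denominator for follow-up and withdrawal rates and for any check of the randomisation.
- Rename the present set *evaluable (at least 3 days)* or *modified ITT*. Where it is used for VAP, report by arm how many were excluded or not assessed, with reasons, so that unassessed patients are not read as free of VAP.
- A pointer to the protocol's meaning of withdrawal, if it has one, would settle the remaining ambiguity.

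The cost is SAP wording and a few extra table rows; no new data are needed. The reported follow-up figure may look less favourable. Outcomes that were never measured are not recovered.

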1.4 Frequency of analysis

There is no planned interim analysis. Statistical analysis will be undertaken after the last participant's follow up.

1.5 Outcome analysis

As a feasibility study, analysis will focus on descriptive statistics and confidence interval (CI) estimation rather than formal hypothesis testing.

1.6 Primary analysis

The aim of this primary analysis is to assess the feasibility of delivering the intervention in the study settings, and selection of primary and secondary outcome measures. Components to be analysed are:

feasibility of a trial by producing:

- CONSORT diagram
- Timing of follow-up assessments
- Time it took to recruit participants
- Number of critical care nurses willing to participate
- Randomization technique effectiveness

feasibility of the intervention by producing:

- Critical care nurses' acceptability of the intervention
- Method of delivering the intervention to each study arm

Selection of primary/secondary outcomes

comparing outcomes of each study group

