1 STATISTICAL ANALYSIS CONSIDERATIONS

1.1 Sample Size

As a feasibility RCT, no formal power calculation will be undertaken (Eldridge et al. 2016). One of the aims of the study is to select the most appropriate primary and secondary outcome measures and inform the sample size for calculation of the future RCT. There is no consensus on the feasibility study recommended number of participants, suggested numbers ranging from 20 -70 (Whitehead et al., 2016). Therefore, this feasibility study aims to recruit 60 participants.

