1.2 Statistical Analysis

Participants will be recruited for a minimum of three days and a maximum of eight days. The planned recruitment period is three-six months. Participants initial evaluation will be on the 3rd day of ICU admission and the second one will be on the 6th day. The follow-up rate is estimated to be 50% or more. An extended CONSORT flow diagram will be used to present descriptive data on screening, enrolment, intervention allocation, and follow-up. It will also show any deviations from protocol, for example, participants developed any unexpected side effects. The modified CPIS will be calculated for each study participant within each study group to compare VAP incidence in each group which will be represented through cross tables and figures. Other descriptive data findings will be also represented through tables/figures.

Data will be presented as frequency and percentages (qualitative variables) and mean \pm SD (quantitative continuous variables). Chi-square (x2) will be used for comparison of categorical variables and will be replaced by Fisher exact test (FET) or Mont Carlo Exact test if the expected value of any cell is less than 5. The student's t-test will be used for the comparison of continuous quantitative variables. For continuous quantitative variables that will not normally distributed, Median will be used as a central tendency measure. The Mann Whitney test (Z) will be used to compare the three groups. The difference will be considered significant at P \leq 0.05. Statistical advised will be sought.

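### Section 1.6 ties selection of the main-trial outcomes only to a comparison between groups, which is imprecise at this size and does not show whether an outcome is usable

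*SAP*

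**What the plan says.** Section 1.1 states the purpose: "One of the aims of the study is to select the most appropriate primary and secondary outcome measures and inform the sample size" of the later RCT. Section 1.6 repeats the first half as an aim of the primary analysis: "and selection of primary and secondary outcome measures". It then lists components under three heads: feasibility of the trial, feasibility of the intervention, and selection of outcomes. The third has a single entry, "comparing outcomes of each study group".

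Three other places bear on this:

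- Section 1.2 names one patient outcome: "The modified CPIS will be calculated for each study participant within each study group to compare VAP incidence in each group". It plans percentages and mean with SD as summaries, and between-group tests with a threshold of 0.05 ("The difference will be considered significant at P").
- Section 1.2 also sets the timing ("Participants initial evaluation will be on the 3rd day of ICU admission and the second one will be on the 6th day") and the expected retention ("The follow-up rate is estimated to be 50% or more").
- Section 1.5 puts the emphasis on description and confidence intervals and away from hypothesis tests.

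**The concern.** A stated primary aim is paired with an analysis that does not answer it. Fitness of an outcome for a main trial depends on whether it can be collected at the planned assessments, whether it has enough events or spread, whether scores pile up at an end of the scale, and how hard it is to obtain. A contrast between arms speaks to none of these. An outcome with half its values missing can show a difference, and a complete, well-behaved one can show none.

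The contrast is also noisy at this sample size. If the choice leaned on it, small or moderate differences in apparent effect between candidate outcomes would mostly reflect chance. The information that the study can supply on usability is not named as a criterion.

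**Working it through.** **Inputs from the SAP.** Recruitment target 60 (1.1). Follow-up of at least 50% (1.2), so the floor is 60 x 0.50 = 30; the SAP does not say which assessment this rate covers. The target of 60 comes from a quoted range of 20 to 70, without a formula, so there is no calculation to reproduce.

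**Assumptions.** Two equal arms, as the trial title suggests, so n = 30 or 15 per arm. VAP rate 20% to 40%; the SAP gives none.

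**Precision of the group difference, continuous outcome.** The 95% CI half-width in SD units is t(0.975, 2n-2) x sqrt(2/n).

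- n = 30: 2.002 x 0.258 = 0.52 SD
- n = 15: 2.048 x 0.365 = 0.75 SD

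**Precision of the group difference, VAP.** The half-width is 1.96 x sqrt(2p(1-p)/n).

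| Assumed rate p | 30 per arm | 15 per arm |
|---|---|---|
| 20% | 1.96 x sqrt(0.32/30) = 20 points | 1.96 x sqrt(0.32/15) = 29 points |
| 40% | 1.96 x sqrt(0.48/30) = 25 points | 1.96 x sqrt(0.48/15) = 35 points |

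**Number of arms.** Section 1.2 also says "The Mann Whitney test (Z) will be used to compare the three groups". With three equal arms (20 or 10 per arm), the pairwise half-widths are 0.64 and 0.94 SD, so the conclusion does not depend on which count is right.

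**The tests in 1.2.** A two-sided t-test at 0.05 has power 48% (30 per arm) or 26% (15 per arm) for a true difference of 0.5 SD, and 86% or 56% for 0.8 SD. The imprecision therefore matters for small and moderate effects more than for large ones.

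**What the same patients can estimate about usability.**

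- Completeness, if 80%: 1.96 x sqrt(0.8 x 0.2/N) = 10 points at N = 60 and 14 points at N = 30.
- VAP rate pooled over arms: 1.96 x sqrt(p(1-p)/N) = 10 to 12 points at N = 60 and 14 to 18 points at N = 30.
- Pooled SD (chi-square limits, N-2 degrees of freedom): 95% CI of 0.85 to 1.22 times the estimate at N = 60 and 0.79 to 1.35 times at N = 30.

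The pooled rate has half the half-width of the difference, but it estimates a different quantity. The case for it is that it answers the question asked; its precision is secondary.

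**Other entries in 1.6.** The CONSORT diagram and the timing of follow-up assessments bear on retention. They are listed under feasibility of the trial and describe participants, so they do not give completeness for each candidate outcome.

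**The case against.** The entry in 1.6 can be read as naming an output and not as a decision rule. Reporting each outcome by arm under 1.2 yields percentages, means and SDs, which already carry much of the event-rate and spread information. Section 1.5 restrains testing. A feasibility trial needs no power, and criteria for choosing outcomes may be in the protocol, which is not at hand.

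Much of this stands. The target of 60 without a power calculation is not a fault. The arm-level summaries are planned, and the protocol may hold criteria. What remains is that nothing in the SAP ties those summaries to selection, while the group comparison is tied to it. Section 1.5 changes how the comparison is reported, not the purpose that 1.6 gives it: an interval of plus or minus 0.5 SD is no better a basis for choosing an outcome than a P value.

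Two stronger readings are tempting, and the document supports neither:

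- A reader might infer that the outcome with the largest or a significant difference will be chosen. The SAP does not say so.
- A reader might infer that the main trial will be sized on the observed difference and so be underpowered. Section 1.1 says only that the study will inform the sample size, which a pooled SD or event rate would also do. Any figure for lost power would need a selection rule, a sizing rule, and a number of outcomes with their true effects, none of which the SAP states.

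**Conclusion.** The point holds in a limited form and is minor. The SAP attaches one analysis to outcome selection, and that analysis does not measure whether an outcome is usable. With two equal arms assumed, the difference is known only to within 0.52 SD if all 60 patients contribute, or 0.75 SD at the 30-patient floor. For VAP this is 20-25 or 29-35 percentage points over the assumed 20-40% rate. The 30-patient case is the lower bound of the stated follow-up, not the expected number. The mismatch between aim and analysis does not depend on these assumptions; only the size of the imprecision does.

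**What to change.** In 1.6, replace the group comparison as the basis for selection with the following, for each candidate outcome:

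- completeness at day 3 and at day 6, counted over all enrolled patients, because the population in 1.3 already leaves out withdrawn patients and those followed for under three days;
- event rate or SD pooled across arms, with a 95% CI;
- floor and ceiling effects;
- ease of collection.

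Keep the comparison between groups as descriptive only, with CIs, in line with 1.5. State that the pooled SD or event rate, with its CI carried forward, will inform the main-trial sample size, and that the observed group difference will not. If the protocol already sets such criteria, align 1.6 with them and cross-refer.

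The cost is SAP wording and a few summaries of data already collected. There are two limits. The pooled estimates are themselves imprecise, as the SD intervals above show. And these criteria identify outcomes that are usable, not outcomes that respond to treatment; that judgement has to come from elsewhere.
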